- 5. Associated syndrome, including Marfan Disease or Neurofibromatosis
- 6. Sanders bone age greater than 4
- 7. Thoracic curve less than 35 degrees
- 8. Lumbar curve greater than or equal to 35 degrees
- 9. Unable or unwilling to firmly commit to returning for required follow-up visits
- 10. Investigator judgement that the subject/family may not be a candidate for the intervention

Number Of Subjects

Study Duration

Study Phases:

Screening

Study Treatment

Post-op Follow-Up

The study will be conducted at The Nemours – Alfred I duPont hospital for Children, Division of Orthopedics. Subject inclusion will be based on interest of patients that satisfy the inclusion/exclusion criteria that present to the Orthopedic Clinic. The total study enrollment will be 30 subjects. In the retrospective arm we will aim to enroll all patients who had the tether surgery in the past. The study ends when all patients reach skeletal maturity. Each subject's active participation will last about 5 years after surgery. The entire study is expected to last at least 8 years.

- 1. Screening phase: Subjects will be screened by study staff during a clinical visit in the Orthopedics department. Eligible subjects will be approached and if interested, enrolled during a routine clinical exam.
- 2. Study Treatment: The subject will undergo surgical intervention using accepted standard-of-care anterior approach using the Globus Medical Inc. CreoTM Stabilization System. Vertebral body tethering using screws and Polyethylene Terepthalate cord (Globus Medical, Inc. Reflect/TransitionTM Stabilization System) is investigational.
- 3. Post-operative Follow-up: Subjects will be followed at regular time points at 45 and 90 days post-op during the post-operative phase. Patients will also be seen at visits 180, 365, 730, 1095, 1460, 1825 days post-op during the extended follow-up phase.

Efficacy Evaluations

The primary efficacy evaluation measurement is thoracic Cobb angle (to nearest degree) at the pre-operative visit to Cobb angle during follow-up, especially at two years post-op (POD 730).

Safety Evaluations

We will use phase-specific endpoints to measure safety: 1) Study treatment phase: Any individual-level intraoperative events including neuromonitoring events (loss or change in neurological signaling or function), unanticipated events during surgery, and SAEs.

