4.6 Subject Completion/Withdrawal

Subjects may withdraw from the study at any time without prejudice to their care. They may also be discontinued from the study at the discretion of the Investigator for lack of adherence to study treatment or visit schedules, AEs, or due to non-compliance. However, in order to collect important study-related data for this investigational device, as much as is feasible, the Investigator will make efforts to follow-up subjects who do not strictly adhere to timely visit schedules. The Investigator may do this via emails, phone calls, or letters. The Investigator may also withdraw subjects who violate the study plan, or to protect the subject for reasons of safety or for administrative reasons. It will be documented whether or not each subject completes the clinical study. If the Investigator becomes aware of any serious, related adverse events after the subject completes or withdraws from the study, they will be recorded in the source documents and on the CRF.

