6.3.2 Safety Analysis

The safety endpoint will be factors associated with the adverse events in patients that have undergone Anterior VBT Surgery. Variable reporting for adverse event will be dichotomous. Descriptive statistics will be used to report number and type of adverse events. Further, chi-square or fisher-exact test analysis will be used to identify variables that correlate with adverse events following anterior tethering surgery. Further, logistic regression will be conducted to clarify which variables are associated with adverse outcomes. Odds ratio along with confidence intervals will be reported.

All subjects will begin the safety analysis at Study Day 0 (day of surgery). Intraoperative and post-intervention medical events or signs and symptoms of the complications arising after the start of study intervention will be captured using list of common events associated with Anterior VBT Surgery. Adverse signs, symptoms, and/or laboratory abnormalities already existing prior to the baseline visit will be captured in the medical history assessment.

The date of onset, severity, and end date (if relevant) will be documented.

Medical events resulting from any procedure performed in the study will be collected as adverse events (AEs). The event description, date of onset, end date, severity, and outcome will be documented for the study-related AEs. The frequencies of AEs by type, body system, severity and relationship to study intervention will be summarized. SAEs (if any) will be described in detail. A distinction will be made between those AE/SAEs which are "device-related", those which are "not device-related", and those which are "uncertain to be related". "Device-related" complications will include any events directly related to the integrity, safety, or biomechanics of the PET cord. Device-related AE incidence will be summarized along with the corresponding exact binomial 95% two-sided confidence intervals. 22

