8.4 Recording plan for AE / SAEs

Surgery and Post-operative Phase (Day 0 – POD 90):

For these phases, all AEs (including SAEs) will be noted in the study records and reported per IRB and FDA requirements outlined below. The subjects will be encouraged to contact the office with any concerns, and the medical record will be monitored by study staff for indications of AEs.

Extended Follow-up Phase (POD 91-POD 1825):

For this phase, all SAEs will be recorded (regardless of cause). Only AEs which are deemed "device related" will be recorded on study documents and reported per IRB and FDA requirements outlined below. The subjects will still be encouraged to contact the office with any concerns, and the medical record will be monitored by study staff for indications of SAEs or device-related AEs.

Only the AE/SAEs indicated above will be recorded in a patient-specific study binder, kept in the secure Orthopedics research office. The binder will contain a full description of the event, including the nature, date and time of onset, determination of non-serious versus serious, intensity (mild, moderate, severe), duration, causality, and outcome of the event. Hard copies of the primary documents (medical record notes) describing the event and any associated treatment will be printed and kept in the patient-specific study binder. A redundant copy of adverse events will be kept in the study REDCap database and will be maintained by the study team separately from the patient-specific study binder. The study binder will serve as the official record of all Events.

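### Section 6.3.2 summarises device-related AEs, recorded to POD 1825, as a simple binomial proportion with no stated denominator, horizon or rule for subjects lost to follow-up

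*Combined protocol and SAP*

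**What the plan says.** Section 6.3.2 (Safety Analysis) makes the AE variable yes/no: "Variable reporting for adverse event will be dichotomous". It starts every subject's safety analysis on the day of surgery. For device events it then says: "Device-related AE incidence will be summarized along with the corresponding exact binomial 95% two-sided confidence intervals". It does not say over what period the incidence is taken, which subjects form the denominator, or what happens to a subject whose follow-up ends early. No Kaplan-Meier, person-time or cumulative-incidence method appears anywhere in the document.

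The recording plan for AEs and SAEs in Section 8 stops collecting other non-serious AEs at POD 90 but continues device-related AEs to POD 1825. The synopsis (Safety Evaluations) places over-correction, implant failure and re-operation in the extended follow-up phase. Section 6.6.2 defines tether failure as something diagnosed after 3 months.

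Section 4.6 allows follow-up to end early: "Subjects may withdraw from the study at any time without prejudice to their care". It also lets the investigator discontinue subjects, including for AEs or non-adherence to visits. Section 6.3.2 does provide what a time-to-event analysis needs: "The date of onset, severity, and end date (if relevant) will be documented".

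**The concern.** A binomial proportion treats each subject as one complete yes/no observation. That is reasonable over 90 days. Over 5 years, a subject who leaves in year 2 without an event has been observed for less than half the period. Counting that subject as a full event-free observation pulls the estimated 5-year risk down. Removing the subject pulls it up, because subjects who had an event before they would have been lost stay in.

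The plan does not choose between these, so the reported figure can move in either direction through a decision taken after the data are seen. Tether breakage, loss of tension and implant re-operation are the main long-term risks of a permanent implant in a growing child, and they are the events most exposed to this choice.

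**Working it through.** The plan has no expected AE rate, loss rate or precision figure, so there is nothing of its own to reproduce.

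**Inputs from the documents.** N = 30 across both arms (Section 3.3.2); recording window of 5 years (Section 8); 95% two-sided exact interval (Section 6.3.2).

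**Assumptions.** True 5-year device-related risk p = 30% (10% to 40% also tried); loss by 5 years L from 0% to 40%; loss independent of events unless stated.

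**All implanted subjects as denominator, constant hazards.** With a = -ln(1-p)/5 and c = -ln(1-L)/5, the expected proportion is a/(a+c) × (1 - exp(-5(a+c))). For p = 0.30 and L = 0.20: 0.3567/(0.3567+0.2231) × (1 - 0.70×0.80) = 0.615 × 0.44 = 0.271.

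**Same denominator, loss spread evenly over 5 years.** The proportion is (1-L)p + L × (mean of F(t) over 0-5 years). With a constant hazard that mean is 1 - 0.30/0.3567 = 0.159. If events occur evenly over years 1 to 5 only, it is 0.30 × 0.5 × 4/5 = 0.12. For L = 0.20: 0.24 + 0.2×0.159 = 0.272, or 0.24 + 0.2×0.12 = 0.264.

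**Subjects lost event-free dropped.** The proportion is crude/(crude + (1-p)(1-L)). For L = 0.20: 0.271/(0.271 + 0.56) = 0.326.

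Results for a true risk of 30%:

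| Loss by 5 years | All subjects, constant loss hazard | All subjects, even loss | Even loss, events from year 1 | Event-free losses dropped |
|---|---|---|---|---|
| 0% | 30.0% | 30.0% | 30.0% | 30.0% |
| 10% | 28.6% | 28.6% | 28.2% | 31.2% |
| 20% | 27.1% | 27.2% | 26.4% | 32.6% |
| 40% | 23.8% | 24.4% | 22.8% | 36.2% |

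Under the constant-hazard model, for true risks of 10% to 40%, the relative understatement with all subjects in the denominator is about 5% at 10% loss, 10% at 20% loss and 20-21% at 40% loss.

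**Worked example.** Take 30 subjects with events at 1, 1.5, 2.5, 3, 3.5 and 4 years, 6 lost event-free at 2 years, and 18 complete. All-subjects proportion: 6/30 = 20.0% (exact 95% interval 7.7% to 38.6%). Losses dropped: 6/24 = 25.0%. Kaplan-Meier: after two events 28 remain, 22 after the losses, and four more events follow, so survival is 28/30 × 18/22 = 0.764 and 5-year incidence is 23.6%.

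**Simulation at N = 30.** For a true 30%, Kaplan-Meier averaged 30.0% at both 20% and 30% loss, against 27.1% and 25.5% for the all-subjects proportion.

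**Sampling error.** 9/30 has an exact interval of 14.7% to 49.4%, a half-width of (49.4 - 14.7)/2, or about 17 points. The shifts with all subjects in the denominator are about 1 to 7 points.

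**The case against.** Several points against the concern have force.

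- **Direction.** A reader might infer that the bias always favours the device. The documents do not support that. The start of the safety analysis is fixed at surgery for all subjects, but the denominator is not stated, and dropping losses reverses the bias.
- **Horizon.** The quoted sentence sets no 5-year period, and Section 2.1 limits the primary objective to the immediate post-operative period, where the binomial summary is sound. This narrows the point to extended follow-up. It does not remove it, because tether failure as defined in Section 6.6.2 falls after 3 months.
- **Loss may be small.** Families who cannot commit to follow-up are excluded (Section 3.4.2), visits follow the standard-of-care schedule (Section 3.3.1), the study makes efforts to reach subjects who miss visits (Section 4.6), and staff monitor the medical record to POD 1825 (Section 8). A missed visit is not automatically an unobserved event.
- **Retrospective arm.** The synopsis says: "In the retrospective arm we will aim to enroll all patients who had the tether surgery in the past". It is tempting to conclude that these subjects have shorter records. No passage says so, and earlier surgery could equally mean longer ones.
- **Sample size.** In the simulations with independent loss, the exact interval still covered the true risk in about 97-98% of trials. At a true 30% and 20% loss, the root mean square error of the crude figure was √(8.1² + 2.9²) ≈ 8.6 points, against 8.9 for Kaplan-Meier. The gain is therefore freedom from systematic bias and a defined horizon, not greater overall accuracy.
- **Kaplan-Meier is not an unconditional remedy.** When a shared risk factor raised both event and loss hazards, true risks of 33.6% and 38.5% gave Kaplan-Meier 31.5% and 32.8%. It was still closer than the crude 26.5% and 27.4%. If a competing event with a 10% or 20% 5-year risk is censored, a Kaplan-Meier figure of 30% corresponds to a true cumulative incidence of 28.6% or 27.1%.
- **Detection dates.** Failures are found on x-ray at visits with a 90-day grace period. An estimate read at exactly POD 1825 would miss failures found at later in-window visits.

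The last two points shape the fix.

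**Conclusion.** The concern holds in limited form. Section 6.3.2 applies a complete-follow-up method to events recorded over 5 years, in a study that allows early exit, and leaves the denominator and horizon open. On the natural reading, long-term device risk would be understated. On the alternative reading it would be overstated.

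The size is conditional. For an assumed true risk of 30% with all subjects counted, the figure is about 28-29% at 10% loss, 27% at 20% and 24% at 40%, or about 23% at 40% loss if events start only after year 1. With complete follow-up the binomial and time-to-event figures are identical. The documents supply neither a loss rate nor an event rate, so a large understatement cannot be asserted, and every shift here is well inside the sampling error at N=30. The case for changing the plan is that the bias is avoidable, concerns the long-term device risk, and can be removed (given noninformative loss) with data already collected.

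**What to change.** In Section 6.3.2:

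1. Keep the exact binomial 95% interval for Day 0 to POD 90, and state its denominator.
2. For extended follow-up, report time-to-event cumulative incidence with 95% CI, separately for device-related AEs and for implant re-operation, at about 1, 2 and 5 years.
3. Read each estimate at the end of the visit window (for example POD 1825 + 90 = 1915), because failures are detected on x-ray at visits.
4. Censor at last contact. Count implant removal as an event only when it is device-related. Treat other removal, or fusion, as a competing event, using the Aalen-Johansen estimator.
5. Report the number lost to follow-up, and state that the estimate assumes loss is noninformative.

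The cost is SAP wording, since onset dates are already documented. The interval will be slightly wider (simulated standard deviation 8.9 against 8.1 points at a true 30% and 20% loss). The estimate will be somewhat higher than the all-subjects proportion whenever event-free subjects are lost.

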6.3.3 Efficacy Analysis

The primary analysis will be based on an intention to treat approach and will include all subjects who have undergone the intervention.

The endpoint used for efficacy will be change in post-operative Cobb angle compared to preoperative Cobb angle, measured on coronal radiograph of the spine. Considering change in Cobb angle is a continuous variable, repeated measures Anova or t-test will be used to detect any change in Cobb angle post-operatively. Linear regression will be utilized to assess which variables are associated with change in post-operative Cobb angle.

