3 INVESTIGATIONAL PLAN

3.1 General Schema of Study Design

3.1.1 Screening Phase

Subjects will be screened from patients presenting to the orthopedic clinic for routine clinical care. Patients who satisfy the inclusion and exclusion criteria will be approached and presented information about the clinical study. Those subjects and families who are interested in pursuing the clinical study will be enrolled by providing informed consent/assent. Subjects who learn about the study through social media and contact Nemours for additional information will be directed to have a scoliosis clinical appointment. After that they will follow the same research procedure as the subjects who present in the orthopedic clinic for scoliosis care. This phase will last 1 day

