3.1.2 Study Intervention (Surgery)

Enrolled patients who have completed the pre-operative course for anterior spine surgery (Pre-operative SOC and Pre-operative study procedures) will undergo the study intervention comprising implantation of anterior vertebral body screws and PET cord under general anesthesia. This phase will last 1 day (day of surgery). This surgical episode is estimated to last about 5.5 hours; 2.5 hours of anesthesia induction and preparation, 2.5 hours of surgery, and 30 minutes of emergence from anesthesia.

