5.1.4 POD-180, POD-365, POD-730, POD 1095, POD 1460, POD 1825 Follow-up

5.1.4.1 Extended Follow-up Visit

5.1.5 Laboratory Evaluations

5.1.5.1 Pregnancy Testing: Performed at Pre-op Visit only

A urine or blood pregnancy test will be performed for female subjects older than 11 years of age, or any female who has begun menses will be required to complete a urine or blood sample pregnancy test. Results of such testing will be provided to the study participant, unless it is determined that she is unable to understand the significance or implications of a positive test result. In this case, the parent (s) will be informed of the positive result. In the event of pregnancy, the participant will not receive the study intervention. Participants who are found to be pregnant will be advised to contact family planning counseling services.

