8.4.1 Relationship of AE/SAE to study intervention or device

The relationship of each Event to the study intervention should be characterized using one of the following terms in accordance with NEMOURS IRB Guidelines: **definitely, probably, possibly, unlikely or unrelated**. In this case, the "study intervention" in considered to be the surgical intervention and implantation of the medical device (*Anterior vertebral body tethering surgery under general anesthesia with spinal cord monitoring*). This includes (but is not limited to) induction of anesthesia, incision and surgical approach, device implantation, and recovery. **For each SAE, the PI and Safety Officer will make a case-by-case determination on the relationship of the SAE to the study procedure, which will be documented in the study documents.**

There will be further classification of the Event as either "device-related", "not device-related", or "uncertain to be device-related". Device-related adverse events are those events directly related to the integrity, safety, or biomechanics of the implanted device. This can include variables like device breakage or device migration. Other adverse events which are considered not device-related are those that are related to the act of the surgery and medical recovery (anesthesia, incision and surgical approach, post-operative recovery, etc.). This distinction will be indicated in the study documents. For each Event, the PI and Safety Officer will make a case-by-case determination on whether the Event is "device related", "not device related", or "uncertain". An event which is classified as "device related" will be considered an Adverse Device Effect. Adverse device effects have special reporting guidelines, as outlined below.

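### The efficacy set is called intention to treat but is a treated set, and its boundary for abandoned or converted operations is undefined, so efficacy may be overstated

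*Combined protocol and SAP*

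**What the plan says.** Section 6.3.3 sets the efficacy population in one sentence: "The primary analysis will be based on an intention to treat approach and will include all subjects who have undergone the intervention". The endpoint there is change in Cobb angle from before surgery, analysed by t-test or repeated measures ANOVA.

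Three other parts of the protocol bear on who is in that set:

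- **Enrolment.** Under section 3.1.1, interested families "will be enrolled by providing informed consent/assent". This comes before the operation.
- **The intervention.** Section 3.1.2 speaks of "the study intervention comprising implantation of anterior vertebral body screws and PET cord under general anesthesia", and the abstract (Study Interventions and Measures) also describes it as implantation. Section 8.4.1, on the relationship of events to the intervention, is wider: "This includes (but is not limited to) induction of anesthesia, incision and surgical approach, device implantation, and recovery".
- **The retrospective arm.** The synopsis says: "In the retrospective arm we will aim to enroll all patients who had the tether surgery in the past". Section 3.3.2 counts both arms towards the total of 30.

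Section 5.3 separately defines overall study success as a final Cobb angle of 50 degrees or less by skeletal maturity. Section 6 attaches no analysis to that criterion.

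**The concern.** An intention-to-treat set is fixed by entry to the study, not by what happened afterwards. Here membership depends on having undergone the intervention, so the stated property is missing.

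The mismatch matters most for operations that do not go as planned. The synopsis lists, as intraoperative safety endpoints, "neuromonitoring events (loss or change in neurological signaling or function), unanticipated events during surgery, and SAEs". Section 9.3.2.1 lists conversion to spinal fusion among the device risks, without saying when it would occur. No section says how a child counts for efficacy if the operation starts and the tether is not implanted. If such children are left out, they are left out because of events during the investigational operation. Correction would then be described only in children in whom the procedure was technically completed, under a label that tells the reader nobody was removed. The study is open label and led by a sponsor-investigator, so the choice of denominator should not wait until results are known.

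**Working it through.** **Step 1: which children are in the set?** There is no planning figure to reproduce; section 6.4 states that there is no effect size or power analysis. The check is a comparison of definitions.

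| Child | Implantation reading (3.1.2) | Surgical-episode reading (8.4.1) | By enrolment (3.1.1) |
|---|---|---|---|
| Consented, never operated on | Out | Out | In |
| Operation started, tether abandoned | Out | Arguably in | In |
| Converted to fusion at that operation, no tether | Out | Arguably in | In |
| Tether implanted | In | In | In |

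The first row is a real pathway. Section 5.1.5.1 says: "In the event of pregnancy, the participant will not receive the study intervention". Such a child, if already consented, is outside the set on either reading. The middle rows depend on which description of the intervention applies, and section 6.3.3 does not choose.

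**Step 2: how much could the middle rows matter?** Inputs:

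- n = 30 operations. This is the section 3.3.2 total for both arms, used for illustration.
- Baseline Cobb angle 44 degrees, from the retrospective tether series cited in section 1.4.1.
- Correction after fusion 57%, from the comparison of fusion approaches cited in section 1.3.1.
- Assumed, because the documents give nothing: k = 1 to 3 abandoned or converted operations, and tether correction of 40% to 65%. Mean change d in implanted children is then 17.6 to 28.6 degrees.

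Mean change over all operated children = [(n − k) × d + k × c] / n, where c is the change in the excluded children.

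*Abandoned, c = 0.* The implanted-only mean exceeds the all-operated mean by the factor n/(n − k), whatever d is:

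| k | Inflation | All-operated mean when d = 22.0 degrees (50% correction) |
|---|---|---|
| 1 | 30/29 − 1 = 3.4% | 22.0 × 29/30 = 21.3 |
| 2 | 30/28 − 1 = 7.1% | 22.0 × 28/30 = 20.5 |
| 3 | 30/27 − 1 = 11.1% | 22.0 × 27/30 = 19.8 |

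The gap is d × k/30. It runs from 17.6 × 1/30 = 0.6 degrees to 28.6 × 3/30 = 2.9 degrees. With fewer than 30 prospective operations, each case weighs more.

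*Converted to fusion, c = 0.57 × 44 = 25.1 degrees.* The gap is (k/30) × (d − 25.1). At 40% tether correction and k = 3 it is −0.75 degrees; at 65% and k = 3 it is +0.35 degrees. Its sign is not fixed.

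**Step 3: the section 5.3 success criterion.** Assume 3 of 30 not implanted and 24 of 27 implanted children succeeding (exact 95% intervals):

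- Implanted only: 24/27 = 88.9% (70.8 to 97.6).
- Non-implanted counted as not a success: 24/30 = 80.0% (61.4 to 92.3).
- All three fused, ending at 50 degrees or less, and credited under section 5.3 as written: 27/30 = 90.0%.

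The counts are invented for illustration. They show that the Cobb threshold alone would credit a fused child to tethering.

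**Step 4: would any such case occur?** The chance of at least one in 30 is 1 − (1 − p)^30: 26%, 79% and 96% for assumed per-operation rates of 1%, 5% and 10%.

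**The case against.** The strongest reply is that section 6.3.3 does not say the tether must be in place. Section 8.4.1 counts induction, incision and approach as part of the study intervention, and section 6.3.2 treats the intervention as something with a start. On that reading a child anaesthetised for tethering is already in the set. This stands as far as it goes: the defect at the boundary is ambiguity, not a stated exclusion. It does not settle the matter, because section 8.4.1 was written to judge the relatedness of events and lists device implantation among the components.

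Second, with one arm and no comparator there is no randomised comparison to protect, and a treated set is a usual choice. Efficacy is secondary, and the safety analysis starts on the day of surgery, so the event behind an abandoned operation should be visible. This also stands. It limits the importance of the point but does not justify the label or supply the missing rule.

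Third, a reader might infer that the analysis includes only children who received the tether and that efficacy is therefore overstated. The documents do not support that. The first part is one of two readings. The second needs a frequency that the documents do not give, and Step 2 shows that excluding conversions can understate mean change as well as overstate it.

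**Conclusion.** Two things follow from the text without assumptions. The efficacy set is a treated set carrying an intention-to-treat label, and no rule covers operations abandoned or converted in theatre. On the narrower of the two descriptions of the intervention, those children leave the set for a reason tied to the operation, so efficacy may be overstated.

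The size is conditional. Mean Cobb change would be inflated by 3.4% to 11.1% if 1 to 3 of 30 operations were abandoned with zero correction. Conversions to fusion would shift it by −0.75 to +0.35 degrees under the stated baseline and correction values. The success-rate illustration concerns section 5.3, not the continuous endpoint analysed in section 6.3.3, and the plan does not say it will report such a proportion. The primary safety objective is unaffected. The point should be settled before analysis.

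**What to change.** Amend section 6.3.3 as follows, with a matching line in section 5.3:

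1. Drop the intention-to-treat label.
2. Define the efficacy set for the prospective arm as every child in whom anaesthesia was induced for the planned tethering.
3. Include the measured Cobb angles of all these children in the change analysis, whether or not the tether was implanted.
4. For overall study success, count a child not implanted, or fused at that operation, as not a success of tethering. State openly that this changes the section 5.3 definition, which now rests on the Cobb threshold alone.
5. Report the implanted-only result as a supportive analysis labelled as treated.
6. List children who consented but were not operated on, with reasons.
7. Report the retrospective arm separately as a treated set. It is selected on having had tether surgery, so it cannot show prospective failures to implant.

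The cost is a little more analysis, continued collection of radiographs in any child not implanted, and possibly a slightly less favourable efficacy figure. No additional patients are needed.
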